13.6 Descriptive Factors

- Age: < 55yo versus > 55yo
- Gender
- Albumin < LLN: yes/no

13.7 Inclusion of Women and Minorities

This study will be available to all eligible patients, regardless of race, gender, or ethnic origin. There is no information currently available regarding differential effects of this regimen in subsets defined by race, gender, or ethnicity, and there is no reason to expect such differences to exist. Therefore, although the planned analysis will, as always, look for differences in treatment effect based on racial and gender groupings, the sample size is not increased in order to provide additional power for subset analyses.

Accrual Targets					
Racial Categories	Ethnic Categories				Total
	Not Hispanic or Latino		Hispanic or Latino		
	Female	Male	Female	Male	
American Indian/ Alaska Native	2	2	0	0	4
Asian	3	7	0	0	10
Native Hawaiian or Other Pacific Islander	2	10	0	0	12
Black or African American	6	1	0	1	8
White	41	53	3	3	100
More Than One Race	0	0	0	0	0
Total	54	73	3	4	134

Ethnic Categories: **Hispanic or Latino** – a person of Cuban, Mexican, Puerto Rican, South or Central American, or other Spanish culture or origin, regardless of race. The term “Spanish origin” can also be used in addition to “Hispanic or Latino.”

Not Hispanic or Latino

Racial Categories: **American Indian or Alaskan Native** – a person having origins in any of the original peoples of North, Central, or South America, and who maintains tribal affiliations or community attachment.

Asian – a person having origins in any of the original peoples of the Far East, Southeast Asia, or the Indian subcontinent including, for example, Cambodia, China, India, Japan, Korea, Malaysia, Pakistan, the Philippine Islands, Thailand, and Vietnam. (Note: Individuals from the Philippine Islands have been recorded as Pacific Islanders in previous data collection strategies.)

Black or African American – a person having origins in any of the black racial groups of Africa. Terms such as “Haitian” or “Negro” can be used in addition to “Black or African American.”

Native Hawaiian or other Pacific Islander – a person having origins in any of the original peoples of Hawaii, Guam, Samoa, or other Pacific Islands.

White – a person having origins in any of the original peoples of Europe, the Middle East, or North Africa.

14.0 CORRELATIVE AND COMPANION STUDIES

There will be two substudies and all patients are encouraged to participate.

14.1 Pharmacogenetic Studies in Alliance A021501: A021501-PP1

14.1.1 Background

Pharmacogenetics examines inter-individual genetic variability that influences the course of drug action so that medication regimens may be optimized to maximize response, while minimizing drug-induced toxicity. The ability to predict prognosis and efficacy, as well as mitigate adverse drug reactions in oncology is of paramount importance because a majority of chemotherapeutic agents are dosed to their maximally tolerated dose, and possess a narrow therapeutic index between efficacy and toxicity. There is currently a dearth of clinically relevant prognostic and predictive pharmacogenetic markers derived from germline variants that have been translated for incorporation into clinical practice. There is an opportunity to better understand the relationship between germline variants, efficacy, prognosis, and toxicity so that more of these pharmacogenetic markers may be utilized clinically to individualize therapies for cancer patients [40].

This could be particularly helpful in the setting of pancreatic cancer, for example, a disease that is rarely curable at the time of diagnosis and that is almost always associated with survival of little more than a year.

Currently, no biomarkers are available to predict response in patients with this disease, and several targeted therapies have failed to confer a survival advantage. Multidisciplinary efforts have focused on improving tools for early diagnosis and cataloguing the architecture of somatic mutations. In conjunction with these efforts, the interrogation of the germline genome of patients aims at characterizing the constitutive basis of biological systems of fundamental importance for tumor biology, like angiogenesis, inflammation, immunity, and others.

A previous genome-wide association study (GWAS) in 294 pancreatic cancer patients treated with gemcitabine in CALGB 80303 identified several new candidate genes for overall survival (OS) [41, 42]. To discover and validate novel genes and pathways of importance in the biology of pancreatic cancer and the pharmacology of its treatment, we set out to use an external cohort of pancreatic cancer patients from the Mayo Clinic where GWAS information for OS had already been obtained [43].

In the Mayo Clinic patients, three SNPs located in genes (*VDR*, *CMYA5*, *CAMK4*) had an effect on OS concordant with that observed in the CALGB 80303 patients ($p < 0.05$). Consistent with a link between the vitamin D receptor gene (*VDR*) and pancreatic cancer, a common SNP in *VDR* (rs2853564, A>G) was associated with OS in patients from both the Mayo Clinic (HR 0.81, 95% CI 0.70-0.94, $p = 0.0059$) and CALGB 80303 (0.74, 0.63-0.87, $p = 0.0002$). Presence of high pre-treatment levels of endogenous vitamin D interacted with rs2853564 to confer improved OS ($p < 0.01$). rs2853564 increased transcriptional activity in luciferase assays and altered binding of the IRF4 transcription factor to *VDR*. Functional genetic variation in *VDR* affects the survival of pancreatic cancer patients. This effect is potentiated by an interaction with vitamin D levels.

The prognostic value of the rs2853564 *VDR* variant has never been tested in the setting of borderline resectable disease. In addition, a comprehensive survey of the germline DNA variation of patients might inform the discovery of novel candidate

genes and pathways that relate to the pharmacology of treatments and the biology of disease.

14.1.2 Objectives

Primary Objective

To test the effect of the rs2853564 *VDR* variant on the 18 months OS rate using both arms combined. We hypothesize that patients with the GG genotype have worse survival than patients with either the AA or AG genotype.

Secondary Objectives

1. To test an interaction between the rs2853564 *VDR* variant and treatment arm on the 18 months OS rate. We hypothesize that the effect of the rs2853564 *VDR* variant on survival might differ between the two arms.

Statistical Methods: Logistic regression will be used to test this interaction. The response variable will be an indicator for survival at 18 months. The predictor variables will include clinical variables, an indicator for rs2853564 *VDR* variant [GG vs. (AA or AG)] and an indicator for treatment arm, and the interaction between variant and treatment arm.

2. To discover novel candidate genes associated with the 18 months OS rate and severe toxicity of chemotherapy. We hypothesize that the genotyping a large series of common germline variants through a genome wide approach will allow the identification of novel gene markers of survival and severe toxicity.
3. To run association analyses with the many molecular markers identified in the correlative science section of this protocol. We hypothesize that the information on the germline variation of patients will associate with molecular markers that relate to constitutional systems like inflammation, immunity, angiogenesis, stromal functions, and others.

Statistical Methods: Penalized regression methods such as LASSO or elastic net will be utilized to determine combinations of genes that may predict the outcomes. Clinical covariates will be forced into the models. Cross validation will be used in the model building to reduce over-fitting. The logistic framework will be used for dichotomous variables, and a Gaussian or time-to-event framework for continuous or survival outcomes, respectively. We will stay abreast of the literature for modeling strategies that are appropriate for such modeling.

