Fisher's Exact test will be used to assess the association of the GG genotype with worse 18 month OS. With a total sample size of $N=125$ in both arms, and 85% expected rate of consent to this study, we expect a sample size of 106 for this aim. We assume 63% 18 month OS rate (the alternative hypothesis in the primary aim of this trial) and 16% prevalence of the GG variant. We expect $n=17$ GG variant patients. Under these assumptions, a Fisher's Exact test has 82% power to detect a difference of 44% versus 82% (i.e. a delta of 38%) 18 month OS rates between the groups defined by the GG variant. Nonparametric methods such as recursive partitioning for classification, regression and survival trees (RPART) will be used to explore a possible predictive value of the GG genotype (secondary objective 1), and prognostic value of common variants (secondary objective 2) [44]. In secondary objective 4, generalized linear model methods and penalized regression together with cross validation will be used to evaluate the association between germline variation and molecular markers of inflammation, immunity, angiogenesis, and stromal functions in an exploratory fashion.

Similar approaches to *Quality Control and Normalization of Expression Data, Differential expression, Model Building, and Internal Model Validation* will be employed. We will stay abreast of the literature for methods that are appropriate for data analysis. A detailed analysis plan will be formulated prior to actual data analysis.

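### The primary VDR test pools AA with AG although the cited evidence fits a per-allele effect, and its predicted direction cannot be checked because the coded allele is not named

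*Combined protocol and SAP*

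**What the plan says.** Section 14.1.1 reports that a common SNP in VDR ("rs2853564, A>G) was associated with OS in patients from both the Mayo Clinic (HR 0.81, 95% CI 0.70-0.94") also had an effect in the second cohort, "CALGB 80303 (0.74, 0.63-0.87". It adds: "Presence of high pre-treatment levels of endogenous vitamin D interacted with rs2853564 to confer improved OS". The section does not state the coded allele, the reference genotype or the genetic model behind either hazard ratio.

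Section 14.1.2 then gives the primary hypothesis: "We hypothesize that patients with the GG genotype have worse survival than patients with either the AA or AG genotype". Its interaction model codes the variant as a binary indicator, GG against AA or AG.

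Section 14.1.3 says: "Fisher's Exact test will be used to assess the association of the GG genotype with worse 18 month OS". The power statement there assumes 106 consenting patients, 16% GG (17 patients), 63% overall survival at 18 months, and 82% power for 44% against 82%. No alpha or sidedness is given. The same section also names a logistic regression of 18-month OS on the variant and promises a detailed analysis plan before the data are analysed.

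**The concern.** There are two separate problems.

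The first is direction. In A>G notation G is the variant allele, and 16% GG makes it the minor allele as well. A hazard ratio below 1 for such a variant is usually read as a benefit of G, which would make GG the best-survival genotype. The hypothesis says GG is the worst. The plan does not reconcile the two, so a reader of the result cannot tell whether worse survival in GG repeats the association seen in the two cited cohorts or reverses it.

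The second is the genotype grouping. Comparing GG with AA and AG pooled assumes a recessive effect of G. It discards the contrast between AA and AG, who are 84% of the patients. If the cited effect is per allele, the primary test does not match the evidence it is meant to follow up and gives away power in a small sample.

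**Working it through.** **1. The plan's own power.** 125 × 0.85 = 106.25, so 106 patients; 106 × 0.16 = 16.96, so 17 GG and 89 others. Exact power of Fisher's test for 44% against 82%, by full enumeration of the two binomials:

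| Version of the test | Power |
|---|---|
| One-sided 2.5% | 82.9% |
| Two-sided 5%, doubled p-value | 82.9% |
| Two-sided 5%, minimum-likelihood p-value | 86.1% |
| One-sided 5% | 88.7% |

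The stated 82% reproduces, but equally well with a one-sided and a two-sided test, so it does not reveal the intended sidedness.

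**2. The model behind the cited hazard ratio.** Section 14.1.1 gives 294 patients for CALGB 80303 and an interval of 0.63 to 0.87.

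- Observed SE(log HR) = (ln 0.87 − ln 0.63) / (2 × 1.96) = 0.323 / 3.92 = 0.082. As a check, z = ln 0.74 / 0.082 ≈ −3.66, p ≈ 0.0003, close to the stated 0.0002.
- In a Cox model SE ≈ 1/√(D × Var(x)), where D is the number of deaths and x the genotype code. D is not given. D = 294, every patient dead, gives the smallest possible SE.
- Any two-group coding: Var(x) ≤ 0.25, so SE ≥ 1/√(294 × 0.25) = 0.117.
- GG against the rest at 16% GG: Var(x) = 0.16 × 0.84 = 0.134, so SE ≥ 1/√(294 × 0.134) = 0.159.
- Per-allele coding, with G frequency √0.16 = 0.40 under Hardy-Weinberg: Var(x) = 2 × 0.4 × 0.6 = 0.48, so SE ≥ 1/√(294 × 0.48) = 0.084.

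Rounding of the limits (0.625 to 0.875 at the widest, 0.635 to 0.865 at the narrowest) allows an observed SE between 0.079 and 0.086. The per-allele value lies inside that range and every two-group value lies far outside it. A two-group comparison would need at least 1/(0.25 × 0.0823²) ≈ 590 deaths. The Mayo Clinic sample size is not given, so the same check cannot be made there.

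**3. Power lost by pooling.** Assumptions: genotype frequencies 0.36/0.48/0.16 (38/51/17 patients), overall 18-month OS 63%, and proportional hazards, so S_g = S_AA^(HR^g) with Σ f_g S_g = 0.63. For HR 0.74 per G allele this gives 55.9%, 65.1% and 72.7% for AA, AG and GG.

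The score test uses T = Σ t·x − p̄ Σ t·n and V = p̄(1 − p̄)[Σ n·t² − (Σ n·t)²/N], where x counts survivors, t is the genotype code and p̄ is the overall proportion alive. Here p̄ = 0.630.

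- Codes 0/1/2: E(T) = 4.35; V = 0.233 × (119 − 85²/106) = 11.85; expected z = 4.35/3.44 = 1.26.
- GG against the rest: E(T) = 1.66; V = 0.233 × (17 − 17²/106) = 3.33; expected z = 1.66/1.82 = 0.91.

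Exact enumeration of the two-sided 5% score test:

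| Per-allele effect | 0/1/2 coding | GG vs rest |
|---|---|---|
| HR 0.74, G protective | 24.6% | 12.9% |
| HR 0.74, coding reversed (G harmful) | 25.9% | 18.2% |
| HR 0.81, G protective | 14.6% | 8.5% |
| HR 0.81, coding reversed (G harmful) | 15.1% | 11.4% |

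**4. Size of the design effect.** The hazard ratio implied by 44% against 82% is ln 0.44 / ln 0.82 = 4.1. The reciprocals of the cited values are 1/0.81 = 1.23 and 1/0.74 = 1.35. The 82% power therefore belongs to an effect far larger than the cited evidence suggests in either direction.

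**The case against.** The strongest objection is that no contradiction is proven. A reader might infer that the hypothesis runs against both prior cohorts. The documents do not support that, because Section 14.1.1 does not say the hazard ratios belong to G. If they belong to A, the hypothesis agrees with them. The vitamin D sentence does not settle it, since it names no favourable genotype. This stands: what can be said is that the passages conflict on the usual reading and are left unreconciled.

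A reader might also infer that a true replication would be missed. A one-sided 5% Fisher test for worse survival in GG would have only 0.2% power if G were protective with HR 0.74 per allele (0.5% at HR 0.81). That needs both a one-sided 5% test and a protective G. The plan states neither, and a one-sided 5% test would give 88.7% rather than the stated 82%. A two-sided 5% Fisher test would have about 10% (6.5% at HR 0.81) and could detect better survival in GG.

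The objection that a per-allele effect is only an inference does not stand. The plan does not state the model, but a two-group comparison is ruled out for CALGB 80303 by the reported interval and sample size.

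It is also fair to say that PP1 is an optional correlative substudy, that a fuller analysis plan is promised, and that a logistic regression is named as well. These limit the consequences. But the GG grouping is already fixed in the primary hypothesis and the power statement, so the later plan would inherit it unless this text changes.

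**Conclusion.** The point holds in two parts. First, the direction of the primary PP1 hypothesis cannot be reconciled with its cited evidence until the coded allele is named. Second, the primary test uses a recessive grouping although the CALGB 80303 result fits a per-allele effect and cannot come from a two-group comparison. For a per-allele effect of the cited size, additive coding is the more powerful choice under either allele direction: about 25% against 13%, or 26% against 18%, at HR 0.74, with smaller gains at HR 0.81. Both tests remain weak, so the change improves the aim without making it well powered.

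The figures rest on the plan's 106 patients, 16% GG and 63% overall 18-month OS, together with assumed Hardy-Weinberg proportions and proportional hazards. The check on the genetic model takes all 294 patients as deaths, which is the assumption most favourable to a two-group reading. The trial's own primary decision on 18-month OS is not affected.

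**What to change.** 1. In Section 14.1.1, state the coded allele and the genetic model behind 0.81 and 0.74, and make the hypothesis in Section 14.1.2 agree with them or explain why it differs.
2. Make the primary PP1 test a two-sided test at a stated alpha with genotype coded 0/1/2 G alleles, for example within the logistic regression already named in Section 14.1.3. Keep GG against AA or AG as a sensitivity analysis.
3. Restate the power for that test, using genotype-specific rates that average to the assumed overall rate. The present pair does not: 0.16 × 44% + 0.84 × 82% = 75.9%, not 63%. Use the number of patients now expected with Arm 2 closed to enrolment.
4. Describe the result as supporting the earlier data only if its direction matches the stated hazard ratio.

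The assay, samples and patients are unchanged. The cost is revised wording, a new power statement, and some loss of power if the effect is purely recessive. For the plan's 44% against 82%, the same score test gives 72% with 0/1/2 coding and 90% for GG against the rest. For a recessive effect of the cited size (GG HR 0.74) the gap is small, 7.5% against 8.5%. The retained sensitivity analysis covers the recessive case.

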14.1.3 Methods

The germline DNA of patients who have consented to these analyses will be collected from peripheral blood as described in [Section 6.2](#).

Genotyping of the rs2853564 *VDR* variant will be conducted by TaqMan assay (Applied Biosystems, Foster City, CA) per the manufacturer's instructions using a CFX384 Real-Time System (Bio-Rad, Hercules, CA) and performed in the laboratory of [name] at the University of North Carolina at Chapel Hill. Sanger-based DNA sequencing (Mammalian Genotyping Core at the University of North Carolina at Chapel Hill) will be used to validate representative samples and determine thresholds for allelic discrimination. The allele frequency will be compared with those previously reported from the HapMap and 1,000 Genomes

projects. Deviation from Hardy-Weinberg equilibrium ($p < 0.01$ for significance) will be tested to evaluate genotyping accuracy.

Genome-wide genotyping will be performed by the OmniExpress Exome chip, which enables whole-genome genotyping of over 700,000 single nucleotide polymorphism (SNP) loci. This platform gives an outstanding breadth of coverage over the genome for the planned association studies. It will be performed at the Mammalian Genotyping Core at the University of North Carolina at Chapel Hill.

Exome and whole sequencing could be also performed from germline and somatic DNA to detect associations between outcome and rare variants.

Logistic regression will be used to assess the relationship between rs2853564 VDR variant and 18 month OS rate. The treatment assignment and the interaction term between rs2853564 VDR variant and treatment assignment will be entered in the model in order to examine whether the effect of the rs2853564 VDR variant differs between 2 arms.

Fisher's Exact test will be used to assess the association of the GG genotype with worse 18 month OS. With a total sample size of $N=125$ in both arms, and 85% expected rate of consent to this study, we expect a sample size of 106 for this aim. We assume 63% 18 month OS rate (the alternative hypothesis in the primary aim of this trial) and 16% prevalence of the GG variant. We expect $n=17$ GG variant patients. Under these assumptions, a Fisher's Exact test has 82% power to detect a difference of 44% versus 82% (i.e. a delta of 38%) 18 month OS rates between the groups defined by the GG variant. Nonparametric methods such as recursive partitioning for classification, regression and survival trees (RPART) will be used to explore a possible predictive value of the GG genotype (secondary objective 1), and prognostic value of common variants (secondary objective 2) [44]. In secondary objective 4, generalized linear model methods and penalized regression together with cross validation will be used to evaluate the association between germline variation and molecular markers of inflammation, immunity, angiogenesis, and stromal functions in an exploratory fashion.

Similar approaches to *Quality Control and Normalization of Expression Data, Differential expression, Model Building, and Internal Model Validation* will be employed. We will stay abreast of the literature for methods that are appropriate for data analysis. A detailed analysis plan will be formulated prior to actual data analysis.

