13.0 STATISTICAL CONSIDERATIONS

Note: Arm 2 closed to new patient enrollment on 08/13/2018.

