14.2 Imaging Science Studies in Alliance A021501: Alliance A021501-IM1

We propose three imaging correlates for this study. The primary objective of these correlative studies is to prospectively validate prognostic biomarkers derived from imaging. We have reviewed how previous clinical trials in this disease could have benefited from stratification and proper selection [45] [46]. By validating the imaging-based biomarkers in this trial, we can develop a better understanding of the results of this trial and design the next generation of trials with these biomarkers in mind. We have previously shown that standard imaging can correlate with drug delivery in PDAC [36]. Our group has pilot data to suggest that two imaging-based properties independently predict overall survival (OS) outcomes of patients. These measurements are the degree of enhancement in the tumor relative to the normal pancreas (called normalized area under the enhancement curve, NAUC) and a measurement of the morphology of the tumor (called the delta measurement). Our pilot data also indicate that changes in NAUC associate with local control of the tumor, and we hypothesize this observation is due to the

pathological response in the tumor after neoadjuvant therapy. With a planned accrual of 134 patients in this Alliance trial, we will be well powered to prospectively validate our pilot data.

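### Section 14 still states substudy power for two full arms after Arm 2 closed; unless the planned total is still reached, several of the stated powers are not delivered

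*Combined protocol and SAP*

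**What the plan says.** Section 13.0 states "Arm 2 closed to new patient enrollment on 08/13/2018". Section 7.0 adds that treatment of patients already in Arm 2 stopped on the same date. Section 13.2 still plans 124 evaluable patients, 62 per arm, and 134 accrued. Section 13.3 also gives 62 evaluable per arm as the maximum. No section raises Arm 1's target.

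Section 14 carries no closure note. Its power statements are:

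- **VDR variant (14.1.3).** The base is given as "With a total sample size of $N=125$ in both arms". Consent then reduces it to 106, of whom 17 are taken to carry GG, on an assumed "16% prevalence of the GG variant". The claimed power of Fisher's test is 82%, and the effect it refers to is this: "detect a difference of 44% versus 82% (i.e. a delta of 38%) 18 month OS rates". No significance level is given.
- **Imaging overall (14.2).** "With a planned accrual of 134 patients in this Alliance trial, we will be well powered to prospectively validate our pilot data".
- **NAUC (14.2.2).** 80% power at hazard ratio 0.47, one-sided 5%, with 20% of patients in the high group. Accrual is 31 months at 4 per month, which is 124 patients.
- **NAUC ratio (14.2.3).** 60% of evaluable patients resected (74) and 41 events. Power is 80% at hazard ratio 1.55, two-sided 5%, variance one.
- **Delta (14.2.4).** 80% power at hazard ratio 0.51, two-sided 5%, with 40% high delta and the same accrual assumptions as NAUC.

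**The concern.** Each of these powers is driven by the pooled number of patients or deaths. With one arm closed and the other capped at 62, the natural reading is that the pooled number will be below 124, yet the figures stand as if both arms would fill.

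The consequence is one of interpretation. A null VDR, delta or NAUC-ratio result would be read against a power of about 80% that the trial may not have. Sections 14.2.2 and 14.2.4 also make failure to validate a cutoff the trigger for searching for a new one, so an underpowered null would lead directly to data-driven cut-points.

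**Working it through.** **Inputs.** From the documents: 85% consent, 16% GG, 44% versus 82%; 31 months' accrual, 20 months' minimum follow-up, 18-month median in the worse group; the hazard ratios, group shares and test levels above; 41 events at 124 evaluable; 62 evaluable in Arm 1. Assumed: VDR level 0.05 two-sided; exponential survival with uniform accrual; NAUC-ratio events proportional to N. Arm 2 is assumed to be 30 to 50. The lower end is the interim-look size in Section 13.4.1.1, and 50 allows for enrolment beyond it. Like the plan, the imaging figures take no discount for consent.

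**Reproducing the plan at full size**

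- *VDR.* 125 × 0.85 = 106; 106 × 0.16 = 17 GG and 89 others. Full enumeration of Fisher's test at 44% versus 82% gives 82.9% by doubling the smaller tail and 86.1% by the minimum-likelihood p-value. The stated 82% matches the first.
- *Delta.* The probability of death over uniform accrual A and minimum follow-up F is 1 − [exp(−λF) − exp(−λ(A+F))]/(λA). With A = 31 and F = 20 this is 0.730 at median 18 and 0.494 at median 18/0.51. Events = 124 × (0.4 × 0.730 + 0.6 × 0.494) = 73.0. Power = Φ(√(73.0 × 0.6 × 0.4) × |ln 0.51| − 1.96) = Φ(0.86) = 80.5%.
- *NAUC ratio.* Power = Φ(√41 × ln 1.55 − 1.96) = 80.1%. Detectable hazard ratio = exp((1.96 + 0.842)/√41) = 1.55.
- *NAUC.* 84.0 events. Power = Φ(√(84.0 × 0.2 × 0.8) × |ln 0.47| − 1.645) = 86.9% at the stated one-sided 5%, and 79.0% two-sided. The printed 80% therefore has slack at the level the plan specifies.

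Delta and the NAUC ratio have almost no slack: 80.5% and 80.1% against 80%.

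**After closure, Arm 1 = 62**

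| Arm 2 | N | Delta, HR 0.51 (events) | NAUC ratio, HR 1.55 (events; detectable HR) | VDR GG/other | VDR, tail doubling | VDR, minimum likelihood | NAUC, HR 0.47, one-sided (two-sided) |
|---|---|---|---|---|---|---|---|
| 62 | 124 | 80.5% (73.0) | 80.1% (41.0; 1.55) | 17/88 | 81.2% | 86.2% | 86.9% (79.0%) |
| 50 | 112 | 76.4% (65.9) | 76.0% (37.0; 1.59) | 15/80 | 75.2% | 82.0% | 83.8% (74.9%) |
| 42 | 104 | 73.3% (61.2) | 72.9% (34.4; 1.61) | 14/74 | 72.0% | 78.9% | 81.3% (71.7%) |
| 30 | 92 | 68.0% (54.1) | 67.6% (30.4; 1.66) | 12/66 | 65.3% | 72.2% | 77.0% (66.4%) |

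The row with Arm 2 at 62 uses 124 patients, so VDR differs slightly from the plan's 125. At 60% resected, N = 92 to 112 gives about 55 to 67 resections against 74 planned.

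**The case against.** The strongest reply is that the shortfall is inferred. The documents do not say how many patients Arm 2 had at closure, why it closed, or whether the 134 total in Section 13.2 still applies. If about 124 evaluable patients are reached, the pooled powers are essentially as printed. This stands, and it is why the point is conditional. The 62-per-arm cap and the absence of any raised Arm 1 target make a shortfall the more natural reading, but they do not prove one.

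A reader might infer that every Section 14 figure has failed. The documents do not support that. NAUC at its own one-sided 5% still has 81% at N = 104 and 84% at N = 112. Its two-sided values are lower, but the plan does not specify that test. The minimum of 62 patients quoted in Section 14.2.3 does not need two full arms. VDR by minimum-likelihood Fisher is back at 82% at N = 112, though that method starts from 86.1%, so there is still a loss like for like.

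A reader might also infer that the marker-by-arm interaction tests have lost a promised power or are invalid. No power is stated for them. An incomplete Arm 2 lowers their precision but does not invalidate them, and relabelling them descriptive would be a preference.

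Finally, the VDR primary objective pools the arms, and the Section 5.0 calendar keeps survival follow-up for patients off treatment, so enrolled Arm 2 patients still count. The calculation above counts them. Sections 14.1.3 and 14.2.2 to 14.2.4 promise detailed analysis plans, which are a natural place for the update but do not correct the figures now in the protocol. The substudies are optional and no trial decision rule uses their power, which limits the weight of the point.

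**Conclusion.** The point holds in conditional form. Section 14 was not restated after Arm 2 closed, and unless the planned total of about 124 evaluable is still reached, several stated powers are not delivered. The printed delta, NAUC-ratio and VDR powers reproduce on their own inputs, so what is wrong is an outdated N.

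With 62 in Arm 1 and an assumed 30 to 50 in Arm 2:

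- Delta loses about 4 to 12 points from the stated 80%.
- The NAUC ratio also loses about 4 to 12 points, or its detectable hazard ratio rises from 1.55 to between 1.59 and 1.66.
- VDR loses about 8 to 18 points from 82.9% by tail doubling, or about 4 to 14 points from 86.1% by minimum likelihood.
- NAUC stays at 77-84% at its stated level and is largely preserved.

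The loss is nil if the total is reached. With no Arm 2 patients at all, which is not realistic, delta would have 51%. It cannot be said from the documents that the powers are definitely lost, nor that all of them are.

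**What to change.** In Sections 14.1.3 and 14.2 to 14.2.4, replace the two-full-arm inputs (125, 134, 124, 17 GG, 74 resections, 41 events) with the actual Arm 1 plus Arm 2 numbers, and restate each power or detectable effect from them. For VDR, state the significance level and the Fisher p-value convention, so that the new figure can be compared with the old one. Drop or qualify the claim in Section 14.2 that the trial is well powered. Add a sentence that the marker-by-arm interaction tests have reduced precision and no stated power. Section 13.2 should say whether the 134 total still applies.

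The cost is wording and a short recalculation from counts the sponsor should already hold. No extra patients are needed. The stated figures will look less favourable.
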